## 10.2. In-services:

The study pharmacist will provide periodic training to residents on correct use of inhalers available in the VA formulary.

## 11. Blinding:

Because we will only review for recommendations patients whose PCP was in the intervention, it is not possible for anyone on the study team to be blinded for the intervention. Patient self-report outcomes collected over the telephone were collected by a coordinator blinded to the patient's intervention status.

## 12. Outcome and Baseline Assessments

We will assess the following using a combination of data extracted from CDW, EHR chart review, and self-report surveys (Table 1). For patient self-report, we will mail an invitation to complete surveys six weeks after their index discharge. The mailing will include a cover letter informing them that their provider is taking part in the study and asking for their input about their satisfaction with their COPD care and COPD-related health.

The mailing also will include an Information Statement with detailed information about the study. The letter will ask them to either return completed surveys by mail, or to return a postcard indicating they do not want to participate or that they want more information through a telephone call. For those who do not respond after two weeks, we will follow up with a telephone call. For those who prefer, we administered the surveys over the telephone. We describe provider self-report methods below.

## 12.1. Primary outcome measures

**Hospital readmission and mortality:** assess 180 days after the index discharge with a composite measure of any hospital readmission or death.

**COPD specific health status:** measured with the *Clinical COPD Questionnaire (CCQ)*, which consists of 10 items that encompass three domains (symptoms, functional state, mental state). Scores range from 0-to-6 with higher scores indicating better health. The minimally important difference (MID) is 0.39 with a standard error of 0.21.

## 12.2. Secondary measures

### **Secondary outcomes - patient-reported:**

**General health status:** measure using the *Veterans RAND 12 Item Health Survey (VR-12)*, which consists of 12 items yielding a Physical Component Summary (PCS) and Mental Component Summary (MCS) score of 0-100, with higher scores reflecting better health. Our outcome is the PCS score, which has a national mean of 27.0 (SD=8.4) among Veterans admitted for COPD.

**Patient satisfaction:** assess patients' satisfaction with respect to the post-discharge primary care follow-up visit using sections of the *Patient Care Medical Home Survey of Healthcare Experiences of Patients (SHEP)* ([Appendix 3](#)). We will use the 6-item communication, 3-item medication decisions, and the 2-item self-management composite scores, as well as single-item questions covering coordination of care, information, and provider rating.

### **Secondary outcomes - provider experience and perception:**

To assess providers' experience and perception of the intervention, we will use a convergent mixed methods approach, concurrently using quantitative and qualitative measures. For quantitative measures, we developed a brief 10-item survey ([Appendix 4](#)), based on our work with the VA Office of Specialty Care Transformation evaluation, that assessed topics directly relevant to our intervention including satisfaction with the consultation process, workload, patient access to specialty care, and quality of care delivered. Within two weeks of posting recommendations for their first intervention patient, we will email providers asking them to complete this survey on-line. For those who do not respond, we will mail the survey with a return inter-office envelope.

For the qualitative approach, coordinators will conduct semi-structured interviews using scripted, open-ended questions and semi-structured prompts ([Appendix 5](#)) to elicit thick descriptions that capture the depth and breadth of providers' experiences including: acceptability; fit with practice; feasibility and satisfaction with the intervention; and its perceived effectiveness. We will invite providers to participate in the interview after their first intervention patient is discharged. We anticipated needing to interview no more than 30 providers to reach thematic saturation, the point at which no new or novel insights are provided 

### 12.3. Other measures:

**Uptake of care recommendations:** A coordinator will use the finalized recommendations checklist to enter recommendations into the study database. A second coordinator, blinded to the first coordinator's entries, also will enter the recommendations. The coordinators will discuss any discrepancies, clarifying with that week's lead clinician as needed to resolve. Six weeks after an index discharge for a patient of an intervention provider, two study coordinators will independently conduct EHR chart reviews to determine which of the care recommendations have been endorsed and completed by the PCP. They will discuss any determination for which they did not agree and consult with a study investigator for resolution as appropriate.

### **Quality of COPD care:**

Using a composite measure of quality metrics endorsed by the National Quality Forum^20, we will use a combination of data from CDW and EHR chart review to assess the overall quality of COPD care 180 days after discharge. Similar to the approach used by Lindenauer et al., our measure will dichotomized those patients who achieved all of the recommended care processes for which they were eligible (score =1) versus those who did not (score =0). Individual measures may be assessed individually or grouped based on whether they are generic (tobacco use, vaccinations) or COPD specific (medications, spirometry). These recommended processes include:

- Assessment of smoking status
- Referral/counseling for smoking cessation, if current or recent quitter (within 1 year)
- Assessment of resting O2 saturation or PaO2
- Provision of O2 for long-term continuous therapy for patients with SpO2<88% or PaO2<55mhg
- Addition of at least one controller agent (LABA, LAMA, ICS, Roflumilast) when appropriate
- Confirmation of COPD by lung function assessment
- Offer, confirmation or administration of influenza vaccination during appropriate season
- Offer, confirmation or administration of pneumococcal vaccination
- Other inhaled therapy types--date filled
- Systemic corticosteroid therapy types--date filled
- Antibiotic therapy types--date filled
- Other therapy types--date filled

### 12.4. Baseline Characteristics:

- Sociodemographic: patient and provider characteristics at enrollment using a combination of CDW and self-report.

We will use CDW to identify/calculate the following:

- COPD and medications: results from patients' most recent pulmonary function tests and pulmonary medication prescriptions over the past 12 months.
- Days exposed to steroid: number of days a patient was prescribed an oral corticosteroid in the year prior to index admission.
- COPD exacerbations not requiring hospitalization: number of outpatient exacerbations over the year prior to the index discharge, defined by a primary outpatient ICD-9 or ICD-10 diagnosis associated with a clinical event and prescription for an antibiotic and systemic corticosteroid within 2 days of the diagnosis.

- Comorbidities and health status indicators: collected information on common comorbidities that comprised the health inventory checklist used in previous intervention studies for the year prior to and through the index admission:
  - diagnoses for COPD and common co-morbidities such as diabetes, liver disease, chronic heart failure, vascular disease, and the like to include diagnoses that comprise the Charlson comorbidity index
  - number of all-cause admissions
  - number of inpatient COPD exacerbations
  - number of COPD outpatient exacerbation
  - length of admission
  - Intensive care unit hours during index admission

Table 1. Summary and timing of data elements.

	Data element	Source	Timing
Primary Outcomes	Hospital readmission	Record review, CDW, patient self-report, CMS (on early participants)	180 days post index discharge
	Mortality	Record review, CDW	
	Clinical COPD Questionnaire	Patient self-report	6 weeks post index discharge
Secondary Outcomes and other measures	VR-12		
	Patient satisfaction / smoking status		
	Care recommendations	EHR chart review	180 days post index discharge
	Quality of COPD care	EHR chart review, CDW, patient self-report	
	Provider satisfaction	Provider self-report survey	2 weeks after receiving recommendations for intervention discharge
		Interview	After receiving recommendations for intervention patient
Key Characteristics	Patient sociodemographic	Patient self-report and CDW	6-weeks post index discharge
	Provider sociodemographic	Provider self-report and CDW	Enrollment
	Comorbid diagnoses	CDW	1 year prior to index discharge
	All cause hospital admissions		
	Inpatient and outpatient exacerbations		
	-Days exposed to steroid		
	Additional COPD treatments		
	-Oral corticosteroid use prior to admission		
	-Oral corticosteroid dosage at admission		
	-Inhaled medications		
	-LTE inhibitors		
	-PDE-4 inhibitor		

## 12.5. Remuneration:

We remunerated participant \$20 for survey completion. We did not pay providers.

## 13. Analytic Approach

---

Our modified stepped wedge design, through its randomized intervention allocation, offers several advantages to interval validity compared to observational approaches. However, our clustered design also requires additional analytic evaluation compared to a simple two-arm randomized trial. The primary outcome measure is COPD hospital readmission/mortality within 180 days as assessed through the CDW. Time zero for intervention patients is the start of the period when the provider cluster is randomized to receive the intervention. Time zero for control patients is the start of each 30-day period (wedge) while the provider cluster remained unexposed to the intervention. Provider clusters randomized to receive the intervention at later time periods will accrue fewer patients than clusters randomized to earlier periods. We will present the analysis for hospital readmission as the example for the analytic approach that would also apply for our secondary outcome measures.

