## **5. Rationale and objectives**

---

To be successful, health systems require a pragmatic health system-level solution. In this intervention, we propose to realign specialty care to collaborate with primary care teams and focus on patient needs and guideline concordance after discharge from hospital for COPD exacerbation. The intervention was designed to: 1) support primary care teams in the care of patients recently discharged for a COPD exacerbation, 2) utilize population health methods to identify patients at risk of readmission, 3) integrate proactive collaborative care

[figure not shown]
with specialty care and primary care teams 4) deliver care within the context of existing services and ongoing care, 5) leverage data systems and virtual care to facilitate improved delivery, and 6) respect the role of primary care while attempting to minimize their workload. Our goal is to improve 1) patient quality-of-life as measured by the Clinical COPD questionnaire and 2) reduce 180-day hospital readmission and mortality after hospital discharge.

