### 13.1. Models

We will use mixed-effects linear regression or logistic regression as appropriate for the outcome of interest (180-day readmission or death, CCQ Total Score, VR-12 PCS) with clustering by provider:  $g(E(y_i|\mathbf{X}_i, \alpha_{j[i]}) = \mathbf{X}_i\beta + \alpha_{j[i]}$ , where  $y_i$  is the outcome for patient  $i$  and  $\alpha_{j[i]}$  is a random effect for provider  $j$  seen by patient  $i$  such that, across providers, the  $\alpha_{j[i]}$ 's are assumed independently and identically distributed (i.i.d.)  $Normal(0, \sigma_\alpha^2)$ .  $\beta$  is a  $7 \times 1$  vector of fixed effects regression coefficients, and  $\mathbf{X}_i$  is a  $1 \times 7$  vector containing the following fixed effects terms for patient  $i$ : a constant term (identical across patients), an indicator for patient  $i$ 's receipt of the intervention ( $X_i^{Intervention} = 1$  if patient  $i$  received the intervention,  $X_i^{Intervention} = 0$  otherwise), three time-based restricted cubic spline terms for patient  $i$ , the number of days in the past year that patient  $i$  was exposed to systemic corticosteroids, and the number of COPD exacerbations not requiring admission experienced by patient  $i$  in the past year. The logistic link function was used for the 180-day readmission or death GLMM such that  $E(y_i|\mathbf{X}_i, \alpha_{j[i]}) = \pi_i = (e^{\mathbf{X}_i\beta + \alpha_{j[i]}})/(1 + e^{\mathbf{X}_i\beta + \alpha_{j[i]}})$ . The identity link function was used for the CCQ Total Score and VR-12 PCS GLMMs such that  $E(y_i|\mathbf{X}_i, \alpha_{j[i]}) = \mu_i = \mathbf{X}_i\beta + \alpha_{j[i]}$ .

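### Section 13 names one primary outcome while Section 12.1 and Table 1 name two, and no success or multiplicity rule covers the pair

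*Combined protocol and SAP*

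**What the plan says.** The analysis section and the outcome section describe the primary endpoint differently.

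- **Section 13** uses the singular: "The primary outcome measure is COPD hospital readmission/mortality within 180 days as assessed through the CDW". It closes by saying that the approach shown for readmission "would also apply for our secondary outcome measures". CCQ is not named there.
- **Section 12.1**, under a plural heading, lists two primaries. One is a 180-day "composite measure of any hospital readmission or death"; the other is "COPD specific health status", measured by CCQ.
- **Table 1** (Section 12.4) places "Clinical COPD Questionnaire" in its primary block, with a six-week time point, next to readmission and mortality at 180 days.
- **Section 5** gives two goals, better quality of life by CCQ and to "reduce 180-day hospital readmission and mortality after hospital discharge". It does not call either one primary.
- **Section 13.1** models three outcomes side by side without ranking them: "180-day readmission or death, CCQ Total Score, VR-12 PCS". Section 13.2 does the same. Neither restricts readmission by cause.
- **Section 13.3** applies one significance level of 0.05, two-tailed, and gives separate powers for readmission, CCQ and SF-12 of 0.874, 0.874 and 0.889.

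No section gives a success criterion, a test order, an alpha split or a multiplicity method for two primaries. The only remark on adjustment is in the Section 15 change log. It concerns VR-12 PCS after its move to secondary status.

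**The concern.** A reader of Section 13 alone would conclude that the trial has one primary outcome, that it counts COPD readmissions, and that CCQ is secondary. A reader of Section 12.1 would conclude that there are two primaries and that any readmission counts. Both readers would be following current text.

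What is at stake is how the result is read. If one of the two outcomes is positive and the other null, the plan does not say whether the trial succeeded. The choice of headline could then be made after the results are known. If either outcome is allowed to carry the claim at 0.05, the chance of at least one false positive is well above the nominal level.

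**Working it through.** **Which sentence is the outlier**

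| Place | Number of primaries | Event |
|---|---|---|
| Section 12.1 | Two (composite, CCQ) | Any readmission, or death |
| Table 1 | CCQ included | Readmission and mortality as data elements, no cause given |
| Sections 13.1, 13.2 | No ranking | Readmission or death, no cause given |
| Section 13 | One | COPD readmission/mortality |

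Section 13 stands alone on both counts. The same sentence limits the source to the CDW, while Table 1 also lists record review, patient self-report and, for early participants, CMS for readmission. Section 13 then sets time zero at the start of a 30-day period, while Section 12.1 counts 180 days from the index discharge.

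**What alpha the stated power used**

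Inputs from Section 13.3: I = 30 clusters, N = 15 per cluster per interval, readmission 0.40 to 0.36, coefficient of variation 0.1. T = 31 comes from period 0 in Section 7 plus 30 steps. The individual-level variance is not stated, so I assume binomial variance at the mean proportion 0.38.

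- σ² = 0.38 × 0.62 / 15 = 0.015707; τ² = (0.1 × 0.40)² = 0.0016
- U = 1 + … + 30 = 465; W = V = 1² + … + 30² = 9,455
- IU − W = 13,950 − 9,455 = 4,495
- U² + ITU − TW − IV = 216,225 + 432,450 − 293,105 − 283,650 = 71,920
- Var = 30 × 0.015707 × (0.015707 + 31 × 0.0016) / (4,495 × 0.015707 + 71,920 × 0.0016) = 0.03077 / 185.67 = 0.0001657, so SE = 0.01287
- θ/SE = 0.04 / 0.01287 = 3.107
- Power at two-sided 0.05: Φ(3.107 − 1.960) = 0.874, as stated
- Power at two-sided 0.025: Φ(3.107 − 2.241) = 0.807

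The same method gives 0.889 for SF-12 (0.35 to 0.39), also as stated. With variance at the baseline proportion, readmission gives 0.869 and 0.800. Each outcome was therefore powered as a separate test at the full 0.05.

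**Family-wise error for two primaries, each at two-sided 0.05**

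If either outcome can support the claim, the error is 1 − P(|Z₁| < 1.96 and |Z₂| < 1.96) under the null for both:

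- Independent tests: 1 − 0.95² = 0.0975
- Correlation of the test statistics 0.3, 0.5, 0.8 (assumed; the documents give none): 0.095, 0.091, 0.078
- Upper bound under any dependence: 0.05 + 0.05 = 0.10

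With a single primary, or if both must be significant, the chance of a false claim is at most 0.05.

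**The case against.** The case on the other side has four parts.

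- **COPD is shorthand.** Section 4 speaks of a COPD readmission penalty and explains it in the same sentence by 30-day hospital readmissions in general. Section 12.1 defines the event explicitly, and Sections 13.1 and 13.2 carry no cause restriction. This largely stands. A reader might infer that the trial has a second, COPD-specific primary endpoint; the documents do not support that. The word still sits in the sentence that defines the primary outcome, so it needs correcting.
- **The two primaries can be inferred.** Section 12.1, Table 1 and the change-log entry moving VR-12 PCS out of the primary set all fit a composite plus CCQ, and Section 13 presents readmission as an example. This is a fair reading. It leaves Section 13 contradicting Section 12.1, and it supplies no success rule.
- **Table 1 is no contradiction.** One might infer from its separate readmission and mortality rows that the composite was dropped. Its caption describes data elements and their timing, and the two elements have different sources. Separate rows are therefore no defect.
- **Error inflation is conditional.** Powering each outcome at 0.05 is equally consistent with one primary or with a both-must-succeed rule. This stands: the power statement does not show that an either-wins rule was intended.

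**Conclusion.** The point holds. Sections 12.1 and 13 disagree on the number of primary outcomes and, in wording, on the event. No rule says how two primaries lead to a conclusion.

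A reader might infer that the plan runs at a 10% error rate. The documents do not establish that, because they never say that either outcome suffices. The range is from at most 0.05 (one primary, or both required) to 0.0975 with independent tests, bounded by 0.10 (either suffices at 0.05 each). The 0.091 figure rests on an assumed correlation of 0.5.

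Nor does the change-log remark on adjustment settle the matter. It concerns VR-12 PCS only and neither sets nor waives a method for the composite and CCQ.

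The defect is not in the power arithmetic, which reproduces. The models can be run as written; what is missing is a pre-stated reading of a split result.

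**What to change.** Replace the whole primary-outcome sentence in Section 13. If both outcomes are primary and either may support the claim, wording such as this would do:

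> There are two primary outcomes: (1) the composite of death or any readmission to hospital in the 180 days following index discharge, and (2) CCQ total score at 6 weeks. VR-12 PCS is secondary. Family-wise error is held at two-sided 0.05 by Holm: the smaller p-value is tested at 0.025, and the other at 0.05 only if the first is significant.

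Three further edits in Section 13 go with it:

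- Change the closing sentence so that the approach applies to CCQ and to the secondary outcomes.
- Reconcile the CDW-only source with the sources in Table 1.
- Reconcile the time-zero sentences with follow-up counted from index discharge.

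If a single primary or a both-must-succeed rule is intended, state that instead and make Section 12.1 and Table 1 match. No alpha split is then needed.

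The cost is a few sentences and no new data. Under Holm, an outcome tested at 0.025 loses some power: 0.874 to 0.807 for readmission on the plan's formula and inputs. That is illustrative only, because Section 13.3 powers readmission and not the composite, and the variance is assumed. I give no figure for CCQ, since Section 13.3 treats a 0-to-6 score as a proportion. Naming one primary costs no power. Requiring both needs no split but makes success harder to reach.

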### 13.1. Models

We will use mixed-effects linear regression or logistic regression as appropriate for the outcome of interest (180-day readmission or death, CCQ Total Score, VR-12 PCS) with clustering by provider:  $g(E(y_i|\mathbf{X}_i, \alpha_{j[i]}) = \mathbf{X}_i\beta + \alpha_{j[i]}$ , where  $y_i$  is the outcome for patient  $i$  and  $\alpha_{j[i]}$  is a random effect for provider  $j$  seen by patient  $i$  such that, across providers, the  $\alpha_{j[i]}$ 's are assumed independently and identically distributed (i.i.d.)  $Normal(0, \sigma_\alpha^2)$ .  $\beta$  is a  $7 \times 1$  vector of fixed effects regression coefficients, and  $\mathbf{X}_i$  is a  $1 \times 7$  vector containing the following fixed effects terms for patient  $i$ : a constant term (identical across patients), an indicator for patient  $i$ 's receipt of the intervention ( $X_i^{Intervention} = 1$  if patient  $i$  received the intervention,  $X_i^{Intervention} = 0$  otherwise), three time-based restricted cubic spline terms for patient  $i$ , the number of days in the past year that patient  $i$  was exposed to systemic corticosteroids, and the number of COPD exacerbations not requiring admission experienced by patient  $i$  in the past year. The logistic link function was used for the 180-day readmission or death GLMM such that  $E(y_i|\mathbf{X}_i, \alpha_{j[i]}) = \pi_i = (e^{\mathbf{X}_i\beta + \alpha_{j[i]}})/(1 + e^{\mathbf{X}_i\beta + \alpha_{j[i]}})$ . The identity link function was used for the CCQ Total Score and VR-12 PCS GLMMs such that  $E(y_i|\mathbf{X}_i, \alpha_{j[i]}) = \mu_i = \mathbf{X}_i\beta + \alpha_{j[i]}$ .

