## 7. Overall Design

Figure 2. Transition of primary care team clusters from control to intervention.

[figure not shown]
\*1-4 providers/team and 2-13 teams/cluster such that each cluster had comparable number of COPD patients

We will perform a modified stepped wedge clinical trial which is a variant of a clustered randomized cross-over design. Our focus will be to evaluate a multifaceted intervention designed to improve quality-of-life and decrease rate of hospital readmission and mortality among patients who were discharged from hospital with an exacerbation of COPD (Figure 2). We chose a modified stepped wedge design for several reasons: 1) resource constraints require a staggered roll out of the intervention; 2) timing is randomized, allowing all providers to eventually receive the intervention; 3) utilizes within and across provider comparisons maximizing efficiency and allowing the fewest number of providers to be enrolled because analyses utilize within provider and between provider comparisons increasing power.

In this stepped wedge design, clusters of teams transition from the control group to the intervention group over time. For this trial (Figure 2), we will assemble 30 clusters of primary care teams (see Section 8.4). Each primary care team consists of between 1-4 primary care clinicians. The number of primary care teams allocated to each cluster will be done to ensure a balanced number of patients with COPD in each cluster. All clusters of teams will start in the control group (first column of Figure 2). At the beginning of every 30-day period, a randomly selected cluster of primary care teams will transition to the intervention group such that all clusters will be in the intervention group in the 30th period (last column of Figure 2). The first control period (period 0) started on May 12, 2015.

We describe the trial flow in the following sections as illustrated in Figure 2.

Figure 2: Overall study flow

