### **8.4. Provider clustering/randomization:**

We will group VA Primary care teams based on continuity and usual cross -coverage purposes. Primary care teams consist of 1-4 providers. We will group consented providers into 30 clusters. When assembling provider clusters, to the extent possible, we will group teams 1) that had shared staffing (e.g. nurses, medical support assistants), 2) are from the same site, and 3) when combined have relatively even distributions of empaneled clinic patients with a COPD diagnosis. By clustering this way, we minimize potential contamination of providers in the control arm by providers who had already crossed into the intervention.

The trial biostatistician will randomly assign each cluster to one of 30 30-day time periods. Each period the next cluster of PCP teams will transition from the control to the intervention period. When new providers join a primary care team, they assume their team's cluster and randomization time period. If providers change teams after randomization, they will retain their original cluster assignment. Any new teams created will be randomly assigned into one of the remaining intervention time periods such that they will have at least one time period in the control and intervention periods.

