### 13.3. Sample size and study power

For the sample size calculation, let the design have  $I$  clusters,  $T$  time points, and  $N$  individuals sampled per cluster per time interval. Assume the model,  $Y_{ij} = \mu + \alpha_i + \beta_j + X_{ij}\theta + e_{ij}$ , where  $\alpha_i$  is a random effect for cluster  $i$  such that  $\alpha_i \sim N(0, \tau^2)$ ,  $\beta_j$  is a fixed effect corresponding to time interval  $j$ ,  $X_{ij}$  is an indicator of the treatment mode in cluster  $i$  at time  $j$  (1=intervention; 0=control),  $\theta$  is treatment effect and  $e_{ij} = \sum_k e_{ij}/N$  are independent and identically distributed  $N(0, \sigma^2)$  and  $\sigma^2_e/N$ . Let  $Y_{ij}$  be the mean for cluster  $i$  at time  $j$ .

Assume testing the hypothesis  $H_0: \theta = 0$  versus  $H_A: \theta = \theta_A$ , where  $\theta_A$  is the treatment effect size. The

approximate power for conducting a two-tailed test of size alpha is  $power = \Phi\left(\left(\theta_A/\sqrt{Var(\hat{\theta})}\right) - Z_{1-\alpha/2}\right)$

where  $\Phi$  is the cumulative standard normal distribution function,  $Z_{1-\alpha/2}$  is the  $(1 - \alpha/2)$ th quantile of the standard normal distribution function and  $\hat{\theta}$  is the estimated treatment effect size. Let  $X_{ij} = 0$  if cluster  $i$  receives the control at time  $j$  and let  $X_{ij} = 1$  if cluster  $i$  receives the intervention at time  $j$ . Thus with this matrix  $\mathbf{X}$  and assuming equal  $N$  per cluster per time interval, then assume  $Var(\hat{\theta}) = [I\sigma^2(\sigma^2 + T\tau^2)]/[(IU - W)\sigma^2 + (U^2 + ITU - TW - IV)\tau^2]$  where  $U = \sum_{ij} X_{ij}$ ,  $W = \sum_j (\sum_i X_{ij})^2$  and  $V = \sum_i (\sum_j X_{ij})^2$ . This variance equation is used in the power calculation. We have approached the power estimates conservatively allowing for a lower proportion of subjects who may experience hospital readmissions, allowing for regression to the mean.

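### The analysis model in 13.1 has a random intercept for provider only, although clusters of teams are randomised and the stated power rests on a cluster effect

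*Combined protocol and SAP*

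**What the plan says.** Section 8.4 groups consented providers into 30 clusters and then states: "The trial biostatistician will randomly assign each cluster to one of 30 30-day time periods". Where possible, clusters combine teams "that had shared staffing (e.g. nurses, medical support assistants") and teams from the same site. Providers stay nested in clusters: "If providers change teams after randomization, they will retain their original cluster assignment". Figure 2 in Section 7 gives "1-4 providers/team and 2-13 teams/cluster", so a cluster holds at least 2 and at most 13 × 4 = 52 providers.

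Section 13 accepts that "our clustered design also requires additional analytic evaluation compared to a simple two-arm randomized trial". The power model in 13.3 contains a term that "is a random effect for cluster", with 30 clusters and a coefficient of variation (CV) of 0.1.

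Section 13.1 specifies the models for "180-day readmission or death, CCQ Total Score, VR-12 PCS) with clustering by provider". The only random effect is an intercept for the provider the patient saw, independent and identically distributed across providers. Neither 13.1 nor 13.2 has a cluster, team or site term, a robust variance, or a sensitivity analysis at cluster level. The change log in Section 15 explains the spline for time and the use of first discharges only. It does not explain why provider rather than cluster is the grouping level.

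**The concern.** A stepped-wedge analysis should allow for correlation at the level that was randomised. Under 13.1, two patients of different providers in the same cluster are independent given the covariates, even though clusters were built from teams that share staff and site, and 13.3 itself assumes that clusters differ. If there is between-cluster variance beyond that between providers, the intervention effect is estimated with less precision than the model reports. Confidence intervals are then too narrow and the test rejects too often. The plan also powers on one variance structure and tests with another, so the stated power does not describe the test specified.

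A smaller matter of wording: 13.1 defines the indicator by receipt of the intervention. Section 13 speaks of clusters "randomized to receive the intervention" and 13.2 is intention-to-treat, so assigned status is the natural reading. No bias is claimed from this.

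**Working it through.** **1. The stated power rests on a cluster effect.** Inputs from 13.3 are I = 30 clusters, N = 15 per cluster per interval, readmission 0.40 v 0.36, CV 0.1 and two-sided alpha 0.05. T = 31 follows from period 0 plus 30 steps. With one crossover per period:

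- U = 1 + 2 + … + 30 = 465, and W = V = 1² + … + 30² = 9,455.
- σ² = 0.38 × 0.62 / 15 = 0.015707, and τ² = (0.1 × 0.40)² = 0.0016.
- Numerator: 30 × 0.015707 × (0.015707 + 31 × 0.0016) = 0.030773.
- Denominator: (30 × 465 − 9,455) × 0.015707 + 71,920 × 0.0016 = 185.67, where 71,920 = 465² + 30 × 31 × 465 − 31 × 9,455 − 30 × 9,455.
- Var = 0.00016573 and SE = 0.012874. Power = Φ(0.04/0.012874 − 1.96) = Φ(1.147) = 0.874, as stated.

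The same steps for SF-12 (0.35 v 0.39) give 0.889, also as stated. Both use τ as the standard deviation between clusters.

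**2. ICC implied by the plan.** 0.04² / (0.4 × 0.6) = 0.0067. The assumed higher values of 0.02 and 0.05 correspond to CVs of 0.17 and 0.27 (√(ICC × 0.24)/0.4).

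**3. Size of the trial.** Section 15 logs about 10 discharges per wedge. That is 10 × 31 = 310 patients, or about 1/3 per cluster-period. The N = 15 in 13.3 would mean 15 × 30 × 31 = 13,950.

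**4. Known-variance calculation (linear model).** A provider-only generalised least squares fit with three spline time terms was given data that truly have cluster variance. The SE ratio is √(sandwich variance / model variance), and type I error is 2 × (1 − Φ(1.96/ratio)). Providers per cluster were 2, 8, 20 and 52. Provider ICC was assumed to be 0, 0.01 or 0.03.

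| Cluster ICC | True/model SE | Type I error |
|---|---|---|
| 0.0067 (plan) | 1.006-1.016 | 5.1-5.4% |
| 0.02 (assumed) | 1.017-1.047 | 5.4-6.1% |
| 0.05 (assumed) | 1.035-1.114 | 5.8-7.9% |

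At N = 15, the plan's ICC and 8-20 providers per cluster, the ratio is 1.095-1.462 and type I error 7.3-18.0%.

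**5. Simulation with estimated variances.** Logistic model, 40% risk, no true effect, Poisson(1/3) discharges per cluster-period, Wald test, 8,000 data sets per setting (Monte Carlo error about ±0.5 points). Each cell lists 8 then 20 providers per cluster at provider ICC 0, then 8 and 20 at provider ICC 0.03. Values are type I error in %.

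| Cluster ICC | Provider only | Cluster only | Cluster + nested provider |
|---|---|---|---|
| 0 | 4.7 / 4.2 / 4.8 / 4.5 | 4.8 / 4.4 / 4.7 / 4.6 | 4.5 / 4.0 / 4.6 / 4.2 |
| 0.0067 | 4.5 / 4.5 / 4.9 / 4.8 | 4.4 / 4.4 / 4.9 / 4.8 | 4.2 / 4.0 / 4.6 / 4.5 |
| 0.02 | 5.9 / 5.1 / 6.0 / 5.4 | 5.4 / 4.7 / 5.6 / 5.1 | 5.3 / 4.2 / 5.4 / 4.6 |
| 0.05 | 7.2 / 6.9 / 6.6 / 6.7 | 5.7 / 5.5 / 5.3 / 5.6 | 5.6 / 5.1 / 5.2 / 5.1 |

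The paired difference, nested minus provider-only, is −0.3 to −0.5 points at ICC 0.0067 (SE 0.08) and −1.4 to −1.8 at 0.05 (SE 0.16). On average 174 or 242 providers have a patient, which is 1.8 or 1.3 patients each. No fit failed to converge.

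**The case against.** The strongest reply is that the plan's own figures show no harm. At CV 0.1 and the logged count, the provider-only model holds its level in simulation. The nested model lies slightly further below 5% in every setting with cluster ICC 0 or 0.0067. This stands: when cluster variance is absent or very small, the proposed model is a little conservative.

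It also stands that clear inflation needs an ICC of 0.05, which the documents do not give. At 0.02, two of the four provider-only results (5.1% and 5.4%) are within Monte Carlo error of 5%. The N = 15 figures describe a trial far larger than the logged count, so they should not be read as the expected effect. The simulation covers only the binary outcome. The CCQ, with its multiple imputation, was not simulated.

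Section 7 does justify the design by comparisons within and between providers, and 8.4 explains the grouping as protection against contamination. Neither makes providers in one randomised cluster independent. The log also does not show that an earlier analysis model had a cluster intercept, so the point is an unexplained mismatch and not a proven change.

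Cluster-only is a close competitor, with 5.3-5.7% at ICC 0.05 against 5.1-5.6% for nested. Nesting is preferred because it keeps the plan's own provider term. With fewer than two patients per contributing provider, that term is the one to give up first.

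**Conclusion.** The concern holds. The primary model omits correlation at the randomised level, and the plan gives no reason for this. No material error is expected at the plan's CV and logged accrual: standard errors are 0.6-1.6% too small with known variances, and simulation shows no excess type I error. At an assumed ICC of 0.05, the provider-only test rejects in 6.6-7.2% of null trials. These results rest on assumed numbers of providers per cluster and assumed provider ICCs, because the documents give only ranges for the former and nothing for the latter.

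The change should be made because the true ICC is unknown when the model is fixed. Leaving out a real cluster component makes intervals too narrow, while including an unneeded one costs little. The wording of the intervention indicator carries no weight in this conclusion.

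**What to change.** In 13.1, include a random intercept for the randomised cluster (30 levels) in the primary model, with provider nested within it. State in advance that provider, not cluster, is dropped if the provider variance is estimated at zero or the nested model does not converge, and that the cluster term stays even if its own variance is estimated at zero. As a clarification, define the indicator as the assigned status, at the index discharge, of the cluster to which the provider was originally assigned, so that it matches 13.2 and 13.3.

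The cost is one more variance component and one reworded definition. Cluster and crossover date are already recorded. At the plan's CV and logged count, standard errors rise by 0.6-1.5% with known variances. In simulation they rise by 2.7-2.9% on average (median 0%), or by 1.9-2.1% on average with no cluster variance. At ICC 0.0067 the cluster variance is estimated at zero in 55-57% of data sets, where the fit equals the provider-only fit. The fallback drops provider in 43-58%, so the rule needs to be written down beforehand.
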